Initial Power Analysis (see amendment below based on reviewer concerns): We intend to screen a total of 1000 patients for up to 10 surgical service lines. Service lines will be randomized 1:1, yielding 500 patients in each treatment arm. Each patient will provide 4 observational units that include preoperative to intraoperative, intraoperative case 1 to intraoperative case 2, intraoperative case 1 to postoperative, and preoperative to postoperative opportunities for detection of *S. aureus* transmission. Thus, 500 patients in each arm will provide 2,000 observational units for a total of 4,000 observational units during the two-year study period. We originally calculated that this provided 90% power to detect a 30% relative reduction in the primary outcome (10.58% down to 7.41%). The estimated clonally related *S. aureus* transmission rate was based on a previously reported detection rate of 58 events in 548 observational units for all-comers to the operating room at 3 major academic medical centers in the United States. To address service line variation, we supposed that the logit-frequencies of the primary outcome for each service line were distributed as a normal distribution with a mean of -0.41 and standard deviation of 0.20. This amount of between-line variation corresponds to an intra-cluster correlation (ICC) of approximately 1%. It can also be interpreted as the amount of variation in which service lines in the top quartile of rates would have an average frequency (after removing within subsection binomial variation) of 46% while service lines in the lowest quartile have an average frequency of 33%. These calculations were accomplished using Monte Carlo simulations written in R 3.3, and using in part the following approximation for the ICC when rates are logit-normal, $1/(1+1/\sigma^2 \cdot \pi^2 \cdot \text{pa}(1-\text{pa}))$ (which can be readily derived using the delta theorem) where pa is the average frequency across centers and σ^2 is the standard deviation on the logit scale. We calculated that this provides 85% power to detect a 30% relative reduction in the primary outcome (40% down to 28%) if there is significant variation between service lines. If indeed there is no variation between service lines, the power is 98%.

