Reducing Perioperative S. aureus Transmission via use of an Evidence-Based, Multimodal Program Driven by an Innovative Software Platform (OR PathTrac)

9/20/2018

Statistical Analysis

Multiple statistical methods were used. For simplification, we list the statistical methods in the precise sequence they are reported in the results.

The Fisher exact test was used to compare patient and procedural demographic information for treatment vs control groups and for cases involving *S* aureus transmission. Similarly, the distribution of patients by ASA scores greater than 2 and by sex for enrolled vs eligible patients were compared by surgeon using the Mantel-Haenszel test.

The Fisher exact test was also used to examine the potential association of each of the covariates mentioned earlier with *S aureus* transmission. None were associated.

A 2-sided Wilcoxon-Mann-Whitney test was used to examine the association of treatment assignment with the number of transmitted *S aureus* isolates. Poisson regression was used to estimate the incidence risk ratio (IRR) of *S aureus* transmission for the independent variable of treatment. Poisson regression was used to estimate the IRR because the incidence of transmission was so large (ie, much greater than 10%) that the odds ratio estimated using logistic regression would be a biased estimator of the relative risk.²⁴ We repeated the analysis using multilevel Poisson regression clustering by surgeon or specialty.

The Fisher exact test was used to compare the proportion of patients in the treatment group with transmission events before vs after surveillance feedback and the proportion of patients with SSI with and without documented *S aureus* transmission. Poisson regression was used to compare the proportion of patients with SSI with and without documented *S aureus* transmission, clustered by surgeon.

The proportion of patients with SSIs was compared with the Fisher exact test. Time to infection was evaluated by Cox proportional hazard modeling. We repeated the analysis using multilevel Poisson regression clustering by surgeon and specialty.

There were no missing data for the primary and secondary outcomes. Calculations were performed using Stata version 16.1 (StataCorp). All P values were 2-sided, and P < .05 was taken to indicate statistical significance.

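### The Poisson model for the transmission IRR has no stated robust or cluster variance, so its interval is wrong: too wide if patients were independent, too narrow under the protocol's own cluster design

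*SAP*

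**What the plan says.** The SAP (Statistical Analysis) states that "Poisson regression was used to estimate the incidence risk ratio (IRR" for transmission, with treatment as the independent variable. The reason given is that incidence was well above 10%, so that "the odds ratio estimated using logistic regression would be a biased estimator of the relative risk". That reason makes sense only for a yes/no outcome. The isolate count is handled separately: "A 2-sided Wilcoxon-Mann-Whitney test was used to examine the association of treatment assignment with the number of transmitted *S aureus* isolates".

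No variance estimator is named for the transmission model. A clustered version follows: "We repeated the analysis using multilevel Poisson regression clustering by surgeon or specialty". By contrast, the Poisson model relating surgical site infection to transmission is itself described as clustered by surgeon.

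The protocol (VI.13) makes the service line the unit of randomization. Section XI.2 gives these planning values:
- "Service lines will be randomized 1:1, yielding 500 patients in each treatment arm".
- A "30% relative reduction in the primary outcome (40% down to 28"%), with power of 85% if lines vary and 98% if they do not.
- Between-line variation with SD 0.20 on the logit scale, described as an ICC of about 1%.
- Separately, "90% power to detect a 30% relative reduction in the primary outcome (10.58% down to 7.41"%), on 2,000 observational units per arm.

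The number of lines is given as up to 10 in the power text and as 6 in the analysis text of the same section.

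**The concern.** Poisson regression is a sound way to obtain a relative risk for a common binary outcome, and the point estimate is not in question. The interval is. Default Poisson standard errors overstate the variance of a 0/1 outcome, and more so as the outcome becomes more common, which is exactly the situation the SAP gives as its reason for using the model. The single-level fit also treats patients in one service line as independent, although whole lines were allocated, and this understates the variance.

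The IRR is the only between-arm effect estimate that the SAP lists for transmission. At stake is whether its confidence interval has anything like 95% coverage.

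**Working it through.** **Plan's own figure.** A two-sided 5% comparison of 40% v 28% with 500 per arm and no line variation gives power of 98.04%, against the stated 98%. The inputs are therefore read correctly.

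**Step 1: independent patients.** Expected events are 500 × 0.40 = 200 and 500 × 0.28 = 140.
- Poisson SE of log RR = √(1/200 + 1/140) = √0.01214 = 0.1102.
- Binomial (sandwich) SE = √(0.60/200 + 0.72/140) = √0.00814 = 0.0902.
- Ratio = 1.221, so the model-based interval is about 22% too wide. A fitted Poisson GLM with default and robust variance returned the same two SEs.

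The ratio depends on the rates. If both arms share one rate p it is 1/√(1−p): 1.18 at 28% and 1.29 at 40%. At 10.58% v 7.41% it is 0.1071/0.1023 = 1.047, or about 5%.

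**Step 2: clustering as the protocol assumes it.** With σ = 0.20 and p = 0.40, ICC = 1/(1 + 1/(0.04 × 0.24)) = 0.0095. This omits the π² factor that appears in the formula as extracted; this reading is the one that gives the stated 1%. Design effect = 1 + (m − 1) × ICC, with equal line sizes.

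| | 10 lines (m = 100) | 6 lines (m = 167) |
|---|---|---|
| Design effect | 1.94 | 2.58 |
| True SE = 0.0902 × √(design effect) | 0.126 | 0.145 |
| Plain Poisson SE / true SE | 0.876 | 0.761 |
| Plain interval too narrow by | 12% | 24% |

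At RR 0.70 the plain interval is 0.564 to 0.869. Using 0.70 × exp(±1.96 × SE) with the clustered SEs gives 0.547 to 0.896 (10 lines) and 0.527 to 0.930 (6 lines), before any small-sample adjustment.

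The two errors cancel at a design effect of 1.221² = 1.49. That is an ICC of 0.49/99 = 0.5% with 10 lines or 0.49/165.7 = 0.3% with 6. Both are below the protocol's value.

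**Step 3: simulation.** 200,000 trials per setting, line rates logit-normal with mean −0.41 and SD 0.20, equal line sizes, one binary outcome per first patient.

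| Type I error | Plain Poisson | Non-clustered robust |
|---|---|---|
| No line variation | 1.2% | 5.0% |
| 10 lines | 6.9% | 15.9% |
| 6 lines | 11.5% | 22.0% |

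Coverage of the plain interval at RR 0.70 is 93.4% (10 lines) and 89.7% (6 lines).

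The simulation applies the treatment effect as a multiplier on each line's rate, which gives slightly less between-line variance in the treated arm than a common ICC does. Its empirical SDs at RR 0.70 are 0.1178 and 0.1337 against model SEs of 0.1105 and 0.1106. That makes the interval 6% and 17% too narrow: same direction, somewhat smaller.

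**Step 4: the multilevel repeat.** A random intercept can only add variance to a within-cluster variance of p. At p = 0.34 the data look overdispersed to a Poisson model only when the design effect exceeds 1/0.66 = 1.52. At ICC 0.0095 that needs about 1 + 0.52/0.0095 ≈ 55 patients per cluster. In smaller clusters, as surgeon clusters may be (their sizes are not given), the random-effect variance tends to zero and the fit falls back to plain Poisson.

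**The case against.** Several objections have force.

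- **The SAP is silent; it does not say that no robust variance was used.** This stands. A reader might infer that default errors were certainly used, but the documents do not show that, and the reference cited for the Poisson choice cannot be consulted here. What can be said is that the model as written carries no such variance, whereas a neighbouring model is described as clustered.
- **A reader might infer that the interval is simply conservative and that power is lost.** At 40% v 28%, rejection would be 94.5% instead of 98.0%, but only with independent patients. The protocol randomizes lines and assumes an ICC of about 1%, which reverses the direction.
- **Poisson is not the named test.** The protocol's primary test is chi-squared and the SAP lists Wilcoxon-Mann-Whitney, so the figures here concern the IRR interval and any P value read from it. The chi-squared test is no refuge: in the same simulation its type I error was 15.9% (10 lines) and 22.1% (6 lines).
- **Clustering is addressed by the multilevel repeat.** Partly. If specialty coincides with service line and clusters are large, the random effect can absorb much of the between-line variance. But it is a repeat and not the main estimate, the level is left as surgeon or specialty, surgeon is not the randomized unit, and no adjustment for few clusters is stated.
- **The 28% to 40% rates are planning values.** True. The SAP says only that incidence was much greater than 10%, so the 22% must be read with its range.

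**Conclusion.** The point holds as a fault in the interval for the transmission IRR, not as a claim that the interval is too wide. Taken as written, the single-level Poisson model gives wrong error bars on either assumption. It is about 22% too wide at 40% v 28% if patients are independent (about 5% at 10.58% v 7.41%). It is about 12% too narrow with 10 lines or 24% with 6 under the protocol's ICC, with type I error of about 7% or 11%. The second case matches the trial's design and is the one to act on.

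The size rests on the protocol's planning rates, an ICC of 0.0095, equal line sizes, 500 first patients per arm and a yes/no outcome per patient. The simulation suggests that the narrowing could be nearer 6% and 17%. At the lower planning rates the Poisson excess is smaller, so it offsets less of any given clustering.

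**What to change.** In the SAP, specify that the transmission IRR is estimated by modified Poisson (or log-binomial) regression with a sandwich variance clustered on the randomized service line. Add a t-based or bias-corrected adjustment for 6 to 10 clusters; a t reference with lines minus two degrees of freedom would have 8 or 4. State the number of lines. If isolate counts are modelled, use the same variance approach. Keep the multilevel model as a sensitivity analysis and fix its level. The SAP is written in the past tense, so if default errors were used, the interval should be re-estimated.

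Do not add a non-clustered robust option alone. It removes the Poisson excess that was partly masking the clustering, and takes type I error to about 16% (10 lines) or 22% (6 lines).

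The drafting cost is a few sentences; the analysis cost is one re-fit plus the small-sample adjustment. The real cost is precision. Under the protocol's ICC the honest interval is wider, and power by design effect is about 82% with 10 lines or 71% with 6, before the small-sample adjustment, against the stated 85%.

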Surgical service lines will include orthopedic total joint, orthopedic spine, gynecology/oncology, thoracic, general, hernia, colorectal, open vascular, plastic, and open urological procedures. These lines will be randomized 1:1 to either the bundle of activities or usual care. The unit of randomization is the service line. The perioperative environment (the patient, the patient to follow, and all providers caring for the patient and the patient to follow) for the randomized service line (treatment or usual care) will be involved in surveillance. This means that all patients, all providers caring for those patients (changes day by day), and care environments (equipment and stopcock sets) will be involved in surveillance. Surveillance from treatment and control groups will yield *S. aureus* transmission events that will be processed to guide proactive improvements in the treatment bundle.

Treatment group (bundle) inclusion/exclusion criteria:

Inclusion criteria: Patients seen at UIHC who are scheduled to undergo surgery from providers in one of the service lines above, documentation of informed, written consent, >18 years of age, procedure requiring general/regional anesthesia.

Exclusion criteria: Lack of documented informed, written consent, patients <18 years of age, procedures outside of the surgical service lines listed above, not requiring general/regional anesthesia, patients not seen in the UIHC clinics, and an allergy to iodine/shellfish or chlorhexidine.

Usual care group (existing practice at UIHC) inclusion/exclusion criteria:

Inclusion criteria: Patients seen at UIHC who are scheduled to undergo surgery from providers in one of the service lines above, documentation of informed, written consent, >18 years of age, procedure requiring general/regional anesthesia.

Exclusion criteria: Lack of documented informed, written consent, patients <18 years of age, procedures outside of the surgical service lines listed above, not requiring general/regional anesthesia, patients not seen at UIHC, and an allergy to iodine/shellfish or chlorhexidine.

VI.14

Provide an estimate of the total number of subjects that would be eligible for inclusion in each of your study populations (include your control population if applicable)

We anticipate that >80% of all patients undergoing surgery in the surgical service lines above will be eligible for the study.

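### The SAP's only cluster-adjusted transmission comparison leaves the cluster level open; its surgeon version sits below the randomised service line and, at the protocol's own ICC, mostly repeats the unclustered result

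*SAP*

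**What the plan says.** Protocol VI.13 is explicit: "The unit of randomization is the service line". It lists ten lines. Protocol XI.2 speaks of six randomised lines in its analysis paragraph and of up to ten in its power paragraph. That power paragraph gives the logit frequencies of the lines a "mean of -0.41 and standard deviation of 0.20" and equates this with an ICC of about 1%.

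In the SAP (Statistical Analysis), transmission is compared between arms by a Wilcoxon-Mann-Whitney test on the number of isolates and by Poisson regression for the risk ratio. Neither accounts for clustering. Poisson is preferred because transmission is common, so that "the odds ratio estimated using logistic regression would be a biased estimator of the relative risk". One sentence then brings in clustering: "We repeated the analysis using multilevel Poisson regression clustering by surgeon or specialty".

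The SAP does not say which level governs or whether both are fitted. It states no robust variance, no small-sample correction and no rule for a variance estimate of zero. It does not define specialty as the randomised line. Its other clustered models concern surgical site infection.

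**The concern.** Every surgeon in a line has the same allocation. A surgeon random effect without a line term treats surgeons of one line as if they had been allocated independently, and it leaves out the line-to-line variation that limits the comparison.

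There is a second difficulty. The stated reason for using Poisson implies a yes/no outcome. A Poisson model gives such an outcome more variance than it has, and that excess can absorb the extra variation from clustering. The random-effect variance is then estimated as zero, and the clustered model becomes the unclustered one.

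This repeat is the only place where the between-arm transmission result is tested against clustering. If it often returns the unclustered answer by construction, its agreement carries little information.

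**Working it through.** **Inputs.** From Protocol XI.2: 40% v 28%, 500 per arm, logit SD 0.20, ten or six lines. From the SAP: two-sided 5% level. Assumed, because the documents do not say: 3, 5 or 10 surgeons per line, equal lines, model-based variance.

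**1. The protocol's figures.** With no between-line variation, the power is Φ[(0.12 − 1.96 × √(2 × 0.34 × 0.66/500)) / √((0.24 + 0.2016)/500)] = Φ(2.06) = 98.0%, as stated. The ICC is 0.04 × 0.24/(1 + 0.04 × 0.24) = 0.0095, also as stated. The 85% figure reproduces as 85.5% with a random-effects z test on ten lines.

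**2. When the random effect vanishes.** At p = 0.40 the Poisson variance per patient is 0.40, while the binomial variance is 0.40 × 0.60 = 0.24. With m patients per cluster, a positive variance is expected only if (1 − p)(1 + (m − 1)ICC) > 1, that is, if ICC > p/[(1 − p)(m − 1)]. For p between 0.34 and 0.40 the threshold is:
- m = 10: 5.7-7.4%
- m = 20: 2.7-3.5%
- m = 33: 1.6-2.1%

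All of these exceed the protocol's 1%.

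**3. False-positive rate when it vanishes.** The analysis is then plain Poisson. Under the null its z statistic has variance 0.24 × (1 + (m − 1) × 0.0095)/0.40, with m now the line size.
- Ten lines, m = 100: 0.24 × 1.94/0.40 = 1.164, SD 1.079. The chance that |Z| exceeds 1.96/1.079 = 1.817 is 6.9%.
- Six lines, m = 166.7: 0.24 × 2.574/0.40 = 1.544, SD 1.243. The chance that |Z| exceeds 1.577 is 11.5%.

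**4. Simulated null trials.** Random-intercept Poisson models were fitted by maximum likelihood with Wald z tests, with 250 to 600 trials per scenario. Ranges are over 3, 5 and 10 surgeons per line.

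| Lines, logit SD | Surgeon variance zero | Unclustered false positives | Surgeon version | Specialty version (taken as the line) |
|---|---|---|---|---|
| 10, 0.20 | 94-100% | 6-7% | 6-7% | 5-6% |
| 6, 0.20 | 85-99.5% | 10.5-13% | 10.5-12% | 8-10% |
| 10, 0.40 (assumed) | 40-94% | 25-27% | 22-25% | 10-12% |
| 6, 0.40 (assumed) | 35-87% | 29-33% | 22-32% | 13-18% |

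At SD 0.20 the surgeon-level standard error was 1.000 to 1.013 times the unclustered one. Even with the line as cluster, the variance was zero in about 60% of trials.

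A larger run (2,500 trials per scenario, five surgeons per line) agrees. At SD 0.20 the surgeon variance was zero in 98.7% (ten lines) and 94% (six). False positives were 7.0% and 10.8% for surgeon and 5.8% and 9.0% for specialty.

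**5. Line-level alternative.** A t test on line proportions with (lines minus 2) degrees of freedom had false-positive rates of 4.9% (ten lines) and 5.0% (six) at SD 0.20. In the larger run it stayed between 5.2% and 5.6% in all four scenarios. Its power for 40% v 28% at SD 0.20 is 72% with ten lines and 49% with six.

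**The case against.** The strongest reply is that the SAP also names specialty, which is close to the randomised line. Its past tense allows the sentence to mean two repeats, one at each level, and the parallel sentence on infection joins surgeon and specialty with *and*. This stands. A reader might infer that the SAP commits to a surgeon-only analysis, but the text does not say so; the defect is that the level is left open. Specialty is not a full answer either, because it is undefined. VI.13 separates total joint from spine, while the pilot table in XI.2 pools orthopaedics.

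A reader might also infer that the false-positive rate is inflated whichever version is run. That is not shown. With ten lines at SD 0.20 the specialty version gave 5.8% and the line t test 5.6%. With a Monte Carlo error of about 0.45 points, the two cannot be told apart. The excess Poisson variance also works in the analysis's favour: it widens the standard error by √(0.40/0.24) = 1.29, which is why even the surgeon version reaches only about 7% there.

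Nor is collapse to zero a general property. It needs a low ICC, small clusters and model-based variance. True surgeon variation of logit SD 0.4 cut it to 43%, and at SD 0.80, suggested by the pilot's 28% to 58% spread, it was 4-41%. The pilot events were not yet clonal, and the protocol expects less variation after genomic analysis. If the plain Poisson used robust standard errors, the two results would not coincide. High collapse and 22-32% false positives should therefore not be joined into one claim: the first belongs mainly to SD 0.20, the second to SD 0.40, which the protocol does not state.

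Finally, this is a sensitivity repeat, and the protocol's primary test is an unclustered chi-squared test. That lowers the severity but does not remove the point.

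**Conclusion.** The point holds in limited form and should be fixed. The SAP permits its only clustered between-arm transmission analysis to be run below the randomised level. At the protocol's own between-line variation, the surgeon version estimates zero variance in about 85-100% of trials and returns the unclustered result, with false positives of about 7% (ten lines) or 11% (six). Its agreement with the unclustered analysis is therefore not evidence of robustness to clustering. If lines vary more (SD 0.40), collapse is less frequent but surgeon-level false positives are about 22-32%.

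The specialty version is adequate with ten lines at SD 0.20 (5-6%). It runs at about 8-10% with six lines and 10-18% at SD 0.40, because it applies large-sample z tests to few clusters.

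These sizes rest on a yes/no outcome (inferred from the SAP's reason for using Poisson), 3 to 10 surgeons per line, equal lines and model-based variance. The mismatch between surgeon and randomised unit rests on none of them.

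**What to change.** For the between-arm transmission comparison, drop the surgeon alternative and name the randomised service line, as allocated, as the cluster. Use a t test on line proportions with (lines minus 2) degrees of freedom and report its matching confidence interval.

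An exact permutation test over allocations is suitable only if the number of lines lets it reach P < .05. With three lines against three there are 20 allocations, so the smallest two-sided p is 2/20 = 0.10. With five against five there are 252, and the minimum is 2/252 = 0.008; power at ten equal lines is then about 69%.

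If surgeon variation is of interest, nest surgeon within line and keep the line term. If any mixed model is retained as support, report its variance estimate so that a zero is visible.

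The change costs SAP wording and a few lines of code, with no new data. The statistical cost is a wider interval: power for 40% v 28% at SD 0.20 is about 72% with ten lines or 49% with six, against the stated 85%.
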